This study was designed to evaluate the efficacy of three different vitamin D supplementation dosages, namely 600 IU, 1200 IU or 4000 IU vitamin D daily for 16 weeks, on both plasma 25(OH)D and parathyroid hormone (PTH) levels among healthy Malaysian women of child-bearing age.

CHAPTER 2: BACKGROUND / LITERATURE REVIEW

2.1. Epidemiologic evidence of vitamin D situation globally, in the region and Malaysia

Micronutrients deficiencies are common globally and serious deficiencies may lead to death (6). The criteria used to defined vitamin D insufficiency in most studies was a serum 25(OH)D level below 50nmol/L (8). Vitamin D insufficiency is especially common amongst osteoporosis patients. A systematic review by Gaugris *et al.* concluded that in post-menopausal women and especially those with osteoporosis and history of fracture showed high prevalence of inadequate 25(OH)D levels (9). A global study of vitamin D status in postmenopausal women with osteoporosis showed that 24 % had 25(OH)D levels less than 25nmol/L, with the highest prevalence reported in central and southern Europe (10). Vitamin D inadequacy is also common among nonwhite populations and populations with low dietary or supplementary vitamin D intake or low exposure to sunlight. A study of Asian adults in the United Kingdom showed that 82% had 25(OH)D levels less than 30nmol/L during the summer season; the proportion increased to 94% during the winter months (11). Even children in sunny countries such as Lebanon are facing common risk with vitamin D inadequacy (12).

Recent studies carried across different countries in South and South East Asia showed widespread prevalence of vitamin D insufficiency in both sexes and all age groups of the population (8). In South India, vitamin D deficiency is equally prevalent among different population groups (13, 14). Vitamin D levels were significantly higher in rural compared to urban subjects in a population-based study (15). Prevalence of vitamin D deficiency in post-menopausal women in Thailand, Malaysia, Japan and South Korea were 47%, 49%, 90% and 92% respectively (8).

A paper by [name] Koon reported that the prevalence of vitamin D insufficiency and deficiency was 27.5% and 19.7% respectively. A total of 856 children aged 4-12 years from six regions of Malaysia were studied. It is found that the serum level of vitamin D among boys ($58.65 \pm 1.46\text{nmol/L}$) was significantly higher compared with girls ($48.95 \pm 1.32\text{nmol/L}$). This study as well found that urban children had lower serum vitamin D level ($52.83 \pm 1.23\text{nmol/L}$) than the rural-living children ($58.14 \pm 1.84\text{nmol/L}$) (16). Another study on school children in Kuala Lumpur, Malaysia by Khor GL *et al.* showed that 35.3% of the children had serum 25(OH)D less than

37.5nmol/L, which indicative of vitamin D deficiency; and another 37.1% had insufficiency vitamin D concentration ($>37.5 - <50$ nmol/L) (6). Study by TJ Green *et al.* on child-bearing age women in Jakarta and Kuala Lumpur reported over 60% of women had a 25(OH)D level of less than 50nmol/L (1). Study on effect of sun exposure on 25(OH)D concentration in urban and rural women in Malaysia indicated rural women has significantly higher 25(OH)D level (69.5nmol/L) compared to urban women (31.9nmol/L) (17). Studies by Foong MM on Malay adults in Malaysia reported that females had significant lower mean 25(OH)D level compared to males (18, 19).

2.2. Factors influencing vitamin D status

In order to maintain adequate vitamin D nutrition in the body, most adults can rely on the natural exposure to sunlight. Malaysia, with the given geographical location near the equator suggested the possibly of having yearlong sunshine. Nonetheless, the prevalence of Vitamin D insufficiency in Malaysia was reported to be considerably high (6, 19, 20). Physical factors that decreased UV-B exposure including clothing, sunscreens, and glass shielding markedly reduce or eliminate production of vitamin D in the skin (21). Cultural practice such as wearing clothing that covers the entire body, applying sunscreen and avoiding direct sunlight may attribute to vitamin D insufficiency/deficiency.

Biological factors that obstruct cutaneous vitamin D synthesis and bioavailability include skin pigmentation, medication use, body fat content and age (4, 21, 22). Cutaneous vitamin D production can be reduced as much as 99.9% with increased skin pigmentation (22, 23). Certain drugs may adversely affect metabolism or bioavailability of vitamin D, for example anticonvulsants, corticosteroids, rifampin, and cholestyramine (10, 24). There are studies shown that body mass index (BMI) and body fat content associated inversely with serum 25(OH)D levels, and directly related to PTH levels. There are limited dietary sources of vitamin D, and obtaining sufficient amount from regular diet is often difficult for many people as the few foods that are rich in vitamin D naturally were not included. Multiple factors including dietary deficiency and decreased cutaneous synthesis due to reduced ability of skin to synthesize vitamin D contribute to vitamin D deficiency among elderly. There has been association between increasing age with lower 25(OH)D levels regardless of season (25).

2.3. Biological relationships between vitamin D, PTH, calcium

The relationship between PTH and serum calcium is bifunctional. PTH regulates the serum calcium concentration while the serum calcium concentration regulates PTH secretion. As such, the stimulation of PTH secretion in response to hypocalcemia acts to restore serum calcium concentration to normal. Vitamin D status is another determinant for basal PTH value. It is widely known that vitamin D deficiency is a cause of secondary hyperparathyroidism (26). Secondary hyperparathyroidism is considered to play significant role in the pathogenesis of age-related bone loss (27, 28). It is also well recognized that serum PTH is the principal systemic determinant of bone remodeling. Although sufficient intake of vitamin D and calcium is important, study by Laufey showed that as long as vitamin D status is secured by vitamin D supplements or sufficient sun exposure, calcium intake of more than 800mg/day may be unnecessary for calcium homeostasis (28). However, there may be other beneficial effects from high calcium intake, such as protective effects in the gut lumen against colon polyp formation (28, 29, 30). Large amount of calcium been showed to be needed to meet body requirement in the absence of active calcium transport in the gut, as in vitamin D insufficiency.

2.4. Importance of sun exposure

This is interesting to understand the relationship of sun exposure and the maintenance of healthy vitamin D level in human body. It is known that sufficient sun exposure is needed to maintain adequate vitamin D level. Literature suggested that vitamin D inadequacy could be due to certain risk factors that influences the amount of UV light reaching skin surface – for example clothing that leaves little skin exposure, heat avoidance and skin colour (1). However, prolonged exposure to sunlight has reported the inverse degradation of vitamin D precursor in the skin, which then, preventing the conversion to the active vitamin. Vitamin D inadequacy in adults leads to secondary hyperthyroidism, increased risk of bone loss and higher risk of osteoporosis. Severe vitamin D deficiency causes muscle weakness, bone pain, and may develop osteomalacia (31, 32).

There is association between obesity with vitamin D deficiency. Regardless of ingested vitamin D from diet or obtained from sun exposure, vitamin D is efficiently deposited in the large body fat stores and is not bioavailable. This could be the possible reason that obese persons are chronically vitamin D deficient (33).

Vitamin D deficiency is characterized by inadequate mineralization or demineralization of the skeleton. However, effects of vitamin D are not limited to mineral homeostasis and skeletal health alone. The presence of vitamin D receptor (VDR) in other tissues suggested the importance of vitamin D in non-skeletal biological processes (31, 32, 34). Studies revealed vitamin D insufficiency in increasing risk of some common cancers, type 1 diabetes, cardiovascular diseases and osteoporosis (31). Grant reported both men and women who received minimum exposure to sunlight are at higher risk of dying of cancer (35).

At this point of time, the establishment of sun exposure recommendation is crucial but again has been challenging due to the lack of subjective measurement for sun exposure. In research, self-reported sun exposure is commonly used, but how well does the information represents actual sun exposure is poorly understood (36, 37). Until recently, the development of sunlight exposure measurement questionnaire (SEM-Q) in Pakistan showed good correlation between sun exposures against quantified exposures from UV dosimeters. The SEM-Q is recommended as a valid tool for epidemiological studies to quantify sunlight exposure (38). To date, there is only one article in Malaysia that has reported the assessment of sun exposure among Malaysian female adults (17). With the recent establishment of SEM-Q, it now leads to the validity of SEM-Q in local context given the difference in latitude, seasons (lack of) the variance in skin pigmentation and polymorphism in vitamin D receptor. These are among the factors identified affecting vitamin D synthesis. Hence, there is this need to have a validated tool to quantify sun exposure, in order to allow the recommendation of sun exposure duration to raise vitamin D to sufficient level to be determined within the local context.

2.5. Vitamin D Supplementation

Dietary vitamin D plays important role as an essential source for individuals who are unable to go outdoors frequently. Currently, the lack of availability of database on Vitamin D content in locally available food impedes the Vitamin D research. Hence, there has been no local data on vitamin D intake among Malaysian. As a result, assessment of vitamin D intake is crucial and serves as a basis to warrant vitamin D supplementation or fortification.

Health authorities in the European Union and the U.S. have set adequate intake levels of vitamin D between 400 and 600 IU/day for adults. With sun-deprived lifestyle resulting in low vitamin D synthesis in the body is the major factor for insufficient vitamin D status. Expert panels in vitamin D research have proposed 25(OH)D blood plasma level of above 75nmol/L as the optimal level. To achieve this level, supplementation studies showed that a vitamin D intake of at least 800 – 1000 IU/day is required by adults.

As based on studies, vitamin D supplementation has been estimated to prevent vitamin D deficiency in approximately 98% of general population (39). Both vitamin D supplementation and sunlight exposure have been shown to increase serum 25(OH)D levels in elderly. To protect against bone diseases and other kinds of degenerative and autoimmune diseases, adequate intake of vitamin D are very important. The Institute of Medicine (IOM) as well as the 2011 Food and Nutrition Board revised and recommended adequate intake of vitamin D up to age 70 is 600IU/day (40). Adults aged more than 70 years required 800IU/day. The upper limit (UL) for vitamin D has been revised and updated to 4,000IU/day. This dosage is defined as the highest level of daily consumption that causes no side effects in humans when used indefinitely without medical supervision (41).

It has been suggested that amounts up to 4,000IU/day of vitamin D may be needed to maintain a healthy 25(OH)D level, an intake of 400IU/day may represent a minimum. There is no reported vitamin D toxicity from long-term exposure to sunlight and no published studies showing adverse effects from dietary intake of 10,000IU dosage. This dose had been set as the No Observed Adverse Effects Level (NOAEL). Doses of 4,000IU/day for 3 months and 50,000IU/week for 2 months have been administered without toxicity (39). The European food safety authority and the US health authority have set 4000 IU/day of vitamin D as the tolerable upper intake level for adolescents and adults.

CHAPTER 3: RESEARCH OBJECTIVES AND HYPOTHESIS

Objectives

1. To determine the efficacy of vitamin D supplementation on plasma 25-hydroxyvitamin D [25(OH)D] and intact parathyroid hormone (PTH) concentrations after daily intake of supplements containing 500 mg calcium with either 0 IU, 600 IU, 1200 IU or 4000 IU vitamin D for 16 weeks.
2. To assess the influence of key covariates, namely sun exposure, vitamin D dietary intake and body mass index status on plasma 25-hydroxyvitamin D [25(OH)D] and intact parathyroid hormone (PTH) of the study participants at baseline and at 16 weeks of supplementation.

Hypothesis

1. H_0 : No significant differences in mean plasma 25-hydroxyvitamin D [25(OH)D] concentrations of participants consuming daily 500 mg calcium and vitamin D supplements at 0 IU, 600 IU, 1200 IU or 4000 IU for 16 weeks
2. H_0 : No significant differences in mean plasma intact parathyroid hormone (PTH) concentrations of participants consuming daily 500 mg calcium and vitamin D supplements at 0 IU, 600 IU, 1200 IU or 4000 IU for 16 weeks
3. H_0 : No significant influence of sun exposure duration, dietary intake of vitamin D and body mass index on plasma 25-hydroxyvitamin D [25(OH)D] and intact parathyroid hormone (PTH) of the study participants at baseline and at 16 weeks of supplementation

CHAPTER 4: METHODOLOGY

4.1. Trial Design

This study is a stratified control trial study. It is a double-blind design, with participants randomly assigned to receive vitamin D doses of 0 IU/day, 600 IU/day, 1200 IU/day, or 4000 IU/day. The study protocol and ethics will first require approval from the International Medical University Joint Research and Ethics Committee (IMU-JC). Consent letter will be given to participants to obtain permission to participate in the study. Reasons and purpose of the study, study protocol and privacy and confidentiality will be informed. All participation shall remain as voluntary.

4.2. Participants

The eligible participants for the study are women of 3 major ethnicity (Malay, Chinese, Indian), age ranged between 20-45 years old with healthy thyroid hormone level. Participants with chronic diseases or medications thought to affect vitamin D metabolism such as hormonal use, thiazide diuretics, prednisolone, biphosphonates, tamoxifen, phenytoin, major gastrointestinal surgery, and primary hyperparathyroidism will be excluded from this study. Pregnant and lactating women will be excluded from this study as well. Participants will be covered with insurance in this research.

4.3. Study setting

The target study population is group of academic and support staffs and universities students in Klang Valley. A total of 120 women subjects from each major race (Malay, Chinese, Indian) in Malaysia will be recruited.

4.4. Intervention

a) Socio-demographic form and anthropometry measurements

A short questionnaire enquiring socio-demographic characteristics, medical history, and usage of supplementations will be given and self-administered by the participants. This served as the first-line screening of participants to confirm that the participants are free from any medications or supplementations that are known to interfere with vitamin D or

calcium metabolism. Anthropometric measurements of weight, height and waist circumference will be measured. The weight of participants will be measured using TANITA digital scale. Participants will be asked to stand on the middle of the weighing scale with barefoot, head looking straight, arms by the side and with light clothing. Then the weight will be recorded and two measurements will be taken to obtain mean body weight. The height will be measured using SECA microtoise. The microtoise will be placed to a smooth surface wall. Then, it will be calibrate until the reading is 0 when pulled on the floor surface. Similar to measuring the weight, participants are required to stand with barefoot, feet with 'v' shape lean against the wall with the heels touching the wall, head placed in Frankfurt Plane and hand by the side. Two measurements will be taken to obtain mean height. By using the mean weight and height, BMI will be calculated to determine the BMI classification of the participants. The waist circumference will be measured using a measuring tape. With the subject in standing position, it will be measure midway between the lowest rib margin and the superior border of iliac crest.

b) To assess vitamin D intake using repeated 24-hour dietary recall

A 2-days 24-hour Diet Record (include 1 weekday, and 1 weekend) will be collected. Researcher will clarify the diet record with the participants upon collection. To allow the participants estimate on portion sizes correctly, photography tools or household measurement tools will be used during the clarification. This is to prevent any under-estimation or over-estimation of portion sizes which may affect the results of the data.

c) To assess sunlight exposure by using Sun Exposure Questionnaire

The sunlight exposure of participants will be determined using a self-administered Sun Exposure Measurement Questionnaire (SEM-Q). It is a validated questionnaire widely used in other countries. Data collected from sunlight exposure measurement questionnaire (SEM-Q) in this study will be correlated with serum vitamin D.

d) Vitamin D supplementation and blood sample

Participants will be randomly divided into groups of 4 for a 16 weeks vitamin D supplementation. One of the group acts as a controlled and the other 3 grouping will be given different amount of vitamin D supplementation of 600IU/day, 1200IU/day and 4000

IU/day respectively. All groups' supplementation included 500mg/day of calcium. Blood collection will be conducted before supplementation as a baseline data, and after 16 weeks of supplementation. The baseline blood draw before supplementation served as the second-line screening of participants. The baseline blood draw served to provides researcher the basal serum 25(OH)D of participants and to exclude any hypo- or hyperthyroidism if detected. Blood drawing will be conducted by trained physicians or phlebotomists after an overnight fast. Blood sample of 5ml will be collected. The serum will be spin down, extracted and stored at -80°C until being analyzed. The serum 25(OH)D, and serum PTH will be analyzed. Serum vitamin D and PTH will be assayed using Centaur Analyser.

The supplements are provided by Fiatec Bioactive Sdn Bhd, Malaysia; where the raw ingredients are imported from DSM Nutritional Products. The products are prepared and packed into vegetable capsules, and will be analyze each to contain at least 90% of the required dosage amount. Vitamin D classification is categorized based on the recommendation of IOM. Serum 25(OH)D level lower than 30nmol/L considered as vitamin D deficiency; and level between 30-50nmol/L considered as vitamin D insufficiency (40). This part of the study is to determine the amount of vitamin required to provide optimum level of PTH, which in turns serves to indicate optimum absorption of calcium.

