4.6. Randomisation: sequence generation

Stratified random sampling method shall be used as it allows equal distribution among each 3 ethnics as well as equal distribution for 4 supplementation groups. Each participant is masked with study code, and only the primary researcher has the master key list. Computer generated randomization of sampling into groups of four shall be used. The sample size will be divided into four groups: Placebo, 600IU/day, 1200IU/day and 4000IU/day. The divided group will then further divided equally into three ethnics group (Malays, Chinese, and Indian). The sampling method is illustrated as below:

[figure not shown]

Diagram 2: Illustration of stratified sampling method

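### Dietary calcium is missing from the covariates named for the PTH regression in Objective 2 and Hypothesis 3

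*Combined protocol and SAP*

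**What the plan says.** Chapter 3, Objective 2, reads "To assess the influence of key covariates, namely sun exposure, vitamin D dietary intake and body mass index status" and applies this list to both 25(OH)D and PTH, at baseline and after 16 weeks. Hypothesis 3 repeats the same three factors. Calcium intake appears in neither.

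On the biology, section 2.3 states: "PTH regulates the serum calcium concentration while the serum calcium concentration regulates PTH secretion". The same section discusses how much calcium intake is needed, and says that the need is large when vitamin D is insufficient.

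On the data, section 4.4(b) collects a two-day diet record, and section 4.11 converts it to energy and nutrient intakes with diet-analysis software. Section 4.11 names multiple regression for relating several independent variables to an outcome. It does not assign calcium intake to any model.

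On the intervention, section 4.4(d) says of all groups: "supplementation included 500mg/day of calcium". Objective 1 carries this background in its wording ("after daily intake of supplements containing 500 mg calcium with either 0 IU, 600 IU, 1200 IU or 4000 IU vitamin D"), and so does the PTH hypothesis ("No significant differences in mean plasma intact parathyroid hormone (PTH) concentrations of participants consuming daily 500 mg calcium and vitamin D supplements").

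**The concern.** Sun exposure, diet and BMI are observed, not assigned. A coefficient for dietary vitamin D in a PTH regression therefore has no protection from randomisation and depends on what else is in the model. The protocol's own background makes calcium a plausible determinant of PTH. Calcium and vitamin D intakes come from the same foods in the same record, so they may well be correlated.

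If they are, and calcium is left out, the dietary vitamin D coefficient absorbs part of the calcium effect. Hypothesis 3 could then be rejected for dietary vitamin D when the relation belongs to calcium.

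The capsules do not remove the problem. At baseline nobody has taken them. At week 16 they add the same planned amount to every woman, which leaves the differences in dietary calcium in place.

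**Working it through.** **Inputs.** The covariate list is from Chapter 3; the 120 women and 30% dropout are from section 4.5. After dropout, 120 × 0.70 = 84. The calcium effect on PTH (b, standardised) and the correlation of the two intakes (ρ) are not in the documents. They are assumptions, shown over a range. Using 120 is also an assumption: section 4.5 gives it as the number to invite, before exclusions, and section 4.3 can be read as 120 per ethnic group.

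**Model.** Let PTH depend on calcium intake with effect b and not at all on vitamin D intake. Leave calcium out. The expected vitamin D coefficient is then b × ρ, with standard error about 1/√n, so

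- δ = |b| × ρ × √n
- false-positive rate ≈ Φ(δ − 1.96) + Φ(−δ − 1.96)

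Example: b = −0.2, ρ = 0.5, n = 120 gives δ = 0.2 × 0.5 × 10.95 = 1.095, and a rate of Φ(−0.865) + Φ(−3.055) ≈ 0.19.

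**Results, nominal level 0.05.** The simulation used 4,000 runs per setting, with two unrelated covariates also in the model.

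| n | b | ρ | δ | Formula | Simulation |
|---|---|---|---|---|---|
| 120 | −0.2 | 0.3 | 0.657 | 0.10 | 0.097 |
| 120 | −0.2 | 0.5 | 1.095 | 0.19 | 0.187 |
| 120 | −0.2 | 0.7 | 1.534 | 0.33 | 0.331 |
| 120 | −0.3 | 0.3 | 0.986 | 0.17 | 0.160 |
| 120 | −0.3 | 0.5 | 1.643 | 0.38 | 0.368 |
| 120 | −0.3 | 0.7 | 2.300 | 0.63 | 0.637 |
| 84 | −0.2 | 0.3 | 0.550 | 0.08 | 0.077 |
| 84 | −0.2 | 0.5 | 0.917 | 0.15 | 0.156 |
| 84 | −0.2 | 0.7 | 1.283 | 0.25 | 0.239 |

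With calcium in the model and no measurement error, the simulated rate is 0.04 to 0.06 in every setting. If ρ = 0, δ = 0 and there is no inflation.

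**Measurement error.** Suppose each recorded intake has reliability 0.5 with independent errors (an assumption). At n = 120 and b = −0.2, the rates for ρ = 0.3, 0.5 and 0.7 are about 0.07, 0.11 and 0.18 without calcium. With recorded calcium added they are about 0.06, 0.07 and 0.09. The problem is smaller, and the cure is incomplete.

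**Price of adjustment.** The variance of the dietary vitamin D coefficient rises by 1/(1 − ρ²): 1.10 at 0.3, 1.33 at 0.5 and 1.96 at 0.7.

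**Sample size.** The stated total of 48 reproduces. A four-group F test with effect size f = 0.7597 and alpha 0.05 has power 0.988 at 44 and 0.994 at 48. The smallest balanced total reaching 0.99 is 48. With one covariate added the minimum moves from 45 to 46, and the balanced total stays 48.

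**The case against.** The strongest reply is that the trial's main comparison is untouched, and that is right. Calcium is the same in every arm, so it cannot confound the randomised dose contrast. Section 4.11 plans ANCOVA between groups, and no within-arm test of PTH is planned.

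A reader might go further and infer that the PTH aim is stated for vitamin D alone. Two sentences omit calcium: the opening statement of the study's purpose ("This study was designed to evaluate the efficacy of three different vitamin D supplementation dosages") and the end of section 4.4(d) ("This part of the study is to determine the amount of vitamin required to provide optimum level of PTH"). Objective 1 and the PTH hypothesis both state the 500 mg background, so the inference fails.

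Nor does the word Placebo in section 4.6 ("The sample size will be divided into four groups: Placebo, 600IU/day, 1200IU/day and 4000IU/day") hide a calcium-free arm. Sections 4.4 and 4.7 both say that all four groups receive calcium.

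Three further replies bear on the regression itself:

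- Section 2.3 ties serum calcium, not calcium intake, directly to PTH, and it also names vitamin D status as a determinant. This stands in part: the link from intake is an inference, though a reasonable one.
- The size rests on assumed inputs and error-free intakes. This stands, and the range above shows how much depends on it.
- Adjustment costs more than one degree of freedom when the intakes are strongly correlated. This stands too, but correlated intakes are also the case in which leaving calcium out misleads most.

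**Conclusion.** The point holds for the non-randomised PTH regressions of Objective 2 and Hypothesis 3, and only there. The named covariate list omits a factor that the protocol's own background links to PTH and that the planned data can supply.

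For an assumed calcium effect of −0.2, correlations of 0.3 to 0.7, 120 women and no measurement error, the false-positive rate for dietary vitamin D is about 0.10 to 0.33 instead of 0.05. Poorly measured intakes bring it closer to 0.05; a stronger calcium effect raises it. With uncorrelated intakes, or no calcium effect, there is no inflation.

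The documents do not support a claim that the shared calcium supplement biases the dose comparison, that the sample size is wrong, or that the formal PTH objective ignores calcium. The loose wording elsewhere is editorial and changes no result.

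**What to change.** Add dietary calcium intake, from the same diet record that supplies dietary vitamin D, as a covariate in the PTH models of Objective 2 and Hypothesis 3, and name it in section 4.11.

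The cost is one degree of freedom and a less precise dietary vitamin D coefficient when the intakes are correlated, with variance about doubled at a correlation of 0.7. A two-day record controls for calcium only in part, and the report should say so. No new data are needed, and the intervention does not change.

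As an editorial alignment only, reconcile the opening purpose statement, the last sentence of section 4.4(d) and the Placebo label in section 4.6 with Objective 1 and Hypothesis 2, which already state the calcium background.
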